4.1 Insulin Pump and DiAs

4.1.1 Equipment Description.

A study insulin pump and DiAs will be provided to all participants at this training visit.

The t:AP research insulin pump will be programmed with the participants' usual pump parameters (basal insulin rate, insulin to carbohydrate ratio, and insulin correction factor) as determined by the study physician. These parameters serve as backup-only settings for the system in open loop mode, and do not determine behavior of the AIDANET algorithm. The bolus priming system (BPS) profile determines the maximum fraction of total daily insulin (TDI) that can be injected by the BPS depending on the time of day (e.g., 8% between 06:00 and 10:00). The BPS profile is a setting on DiAs which can be modified by the provider to impact performance of the AIDANET algorithm. The study physician may alter the BPS profile during the hotel session and At-Home portions of the study to optimize participant safety with the experimental system.

4.1.2 Equipment Training

The purpose of this training visit is to introduce the study system to the participants. Training on the DiAs and study pump may begin when the AIDANET system has been put in place. The participants will be trained in the basic functionality (e.g., bolus menu and infusion set change menu) for the study pump. For the Tandem pump training, a checklist is available on-line with relevant sections applicable to the study pump will be covered. Insulin parameters will be determined by the investigator(s) and programmed into their study insulin pump and confirmed by two research staff. Participants will then switch to the study insulin pump. The participant's personal pump will be removed. The investigator may elect to use an existing personal pump infusion site at their discretion at the start of the study. The participant will be instructed on charging the pump, menu navigation, bolus procedures, and infusion site changes. The DiAs training includes information on charging the phone, maintaining connectivity, menu navigation including bolus procedures and TCR adjustments.

Data-driven optimization of pump or system settings can occur at any time, particularly if the participant contacts the study physician due to concerns about their pump settings due to recurring hypo- or hyperglycemia.

4.2 Continuous Glucose Monitor

4.2.1 Equipment Description

The study CGM will include the Dexcom G6 transmitter and sensor. Participants may elect to wear their personal Dexcom G6 CGM equipment throughout the study period. If currently wearing a G7 CGM model, the participant will be provided with G6 CGM supplies. These sensors may be worn for up to 10 days of continuous wear. The G6 transmitter may be worn for 3 months.

4.2.2 Equipment Training

A study CGM will be provided to all participants as needed prior to or at the training session at Visit 2. Participants using the Dexcom G6 may continue their personal CGM during the study

session. The participants will be provided with CGM equipment and instructed to use CGM on a daily basis. If the participant has prior use of the G6, retraining will be specific to the individual. The study team may elect to have less frequent CGM users watch the Dexcom online training videos (<https://www.dexcom.com/training-videos>) to assist in the training session. Study staff training may include review of the study CGM in real-time to make management decisions and how to review the data after an upload for retrospective review. Study staff will specifically identify how alarms are set using the app and the frequency that these alarms will repeat.

For participants not using the Dexcom G6, the participants will be observed placing the sensor and will learn/review how to access the CGM trace via the Dexcom G6 commercial app (prior to the hotel session) and via the DiAs phone (during the hotel session). The participants will be asked to perform fingerstick blood glucose measurements (if needed) in accordance with the labelling of the study CGM device. An electronic copy of the CGM user's guide will be provided for these participants to read. The study team will be sure that the participants will leave the training session knowing how to properly use the CGM. The study team will be available for any questions.

The study team will ask participants to share their data to the study Dexcom clinical account. This requires a one-time confirmation of data sharing between either the participant's personal Dexcom account or the study Dexcom account and the study clinical account. Participants are identified in the study clinical account by their assigned participant number. The participant does not need to provide the study team with their own login information at any point in this process. The Dexcom clinical account allows the study team to remotely assess and download data as needed. Data sharing between the personal Dexcom account or study Dexcom account and the clinical account can be ended at any time by the participant.

During the study, participants will have the option of using their personal smartphone or receive a study smartphone to use in order to collect the data from the devices. They may also use their own Dexcom G6 or G7 CGM. If the participant elects to use a personal device, the Dexcom app will be downloaded to their phone in order to monitor the participant's CGM values and alerts in real-time may be used prior to initiating DiAs.

4.3 Blood Glucose Meter and Strips

A study glucometer will be provided to all participants to record any blood glucose levels measured during the study. Participants will be advised to use the study glucometer when experiencing a low or high glucose values as defined in the Glycemic Treatment Guidelines. The Dexcom CGM will be calibrated, if needed, using the study glucometer and test strips in accordance with the manufacturer's labeling.

If the study glucometer provides an app, the study team will request that the app be downloaded to the participant's personal phone. The app will permit continued visibility of blood glucose values to the participant and permit the study team to download the data without returning the glucometer at the end of the study.

525 **4.4 Ketone Meter and Strips**

526 Blood ketone levels will be measured during the hotel session and At-Home Period of the study
527 with either the Abbott Precision Xtra Meter or the Ketomojo Meters and ketone test strips in
528 accordance with the manufacturer's labeling. Urine ketone strips may be provided to the
529 participant for the At-Home Period. The glucometer component of either ketone meters will not
530 be used.

531 **4.5 Study Devices Accountability Procedures**

532 Device serial numbers will be recorded, and use of equipment will be tracked.

Chapter 5: AIDANET At-Home Period

5.1 AIDANET use at home

Visit 3

Participants will use the study equipment with the AIDANET algorithm for 7 days/6 nights. Participants will be instructed to follow their normal routine involving diet, exercise, and insulin administration during this week.

Participants using their personal Dexcom CGM will share their CGM download data with the study team at the completion of this week.

Remote monitoring will be in place during this At-Home Period as detailed in section 7.2. Participants will be advised to call the study team if they have any questions or concerns.

Approximately 24-48 hours after initiating the system, the study team will contact the participant via phone/email/text/video to assess adverse events, adverse device effects, and device issues. If the participant chooses, this visit can occur at the clinical site. The study team will verify the following information:

1. Review system use
2. Inquire about any changes to the participant's medical history
3. Inquire about any changes to the participant's medication
4. Review of CGM data
5. Review of hypoglycemic events
6. Review of hyperglycemic events

Any other relevant contacts during the week will be recorded on the CRF and summarized as appropriate (e.g. contact that is not a scheduling or supplies issue will not be recorded).

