INSPIRE & Technology Expectation/ Assessment Survey	X						X (post)	
Randomization	X							
AIDANET use with Remote monitoring		X	X					
AIDANET or AIDANET+ BPS_RL use					X	X		
AIDANET+ BPS_RL 1-week use with Remote monitoring							X	
Check-in visit			X				X	
Review diabetes management and AEs			X	X			X	

Contact type is Clinic Visit and Remote which includes videoconferencing, phone, text messages and emails.

TABLE 2. METRIC CAPTURE TIMELINE

	Enrollment	AIDANET At-Home	Hotel Sessions	AIDANET+ BPS_RL At-Home
Visit	1	3	5 & 6	7
Demographic Data	x			
HbA1c	x			
CGM Data		x	x	x
TIR 70-180 mg/dL		x	x	x
CGM%<54 mg/dL		x	x	x
CGM%<70 mg/dL		x	x	x
CGM%>180 mg/dL		x	x	x
CGM%>250 mg/dL		x	x	x
Mean CGM		x	x	x
Time in Automation		x	x	x
Total Daily Insulin Dose		x	x	x
Number of Boluses per Day		x	x	x
Exercise: CGM %<70 mg/dL		x	x	x
Unannounced Meals: % CGM>250 mg/dL		x	x	x

1	Table of Contents	
2	Chapter 1: Background and Introduction.....	13
3	Chapter 2: Study Synopsis	16
4	2.1 Study Objective.....	16
5	2.2 Specific Aims and Hypotheses	16
6	2.3 Study Design.....	16
7	2.4 Study Hardware/Software.....	17
8	2.5 Timing of Device Use.....	17
9	2.6 Meal Testing	18
10	2.7 Study Devices Download.....	18
11	2.8 Study System Issues.....	18
12	Chapter 3: Study Screening	19
13	3.1 Clinical Site.....	19
14	3.2 Participant Recruitment and Enrollment.....	19
15	3.3 Informed Consent and Authorization Procedures.....	19
16	3.4 Participant Inclusion Criteria	19
17	3.5 Participant Exclusion Criteria	20
18	3.6 Screening Procedures.....	21
19	3.7 Screen Failures / Participant Dropout	22
20	3.8 Personal Equipment Downloads	22
21	3.9 Surveys.....	22
22	3.10 Other Considerations	22
23	3.11 Randomization	23
24	Chapter 4: Study Devices & Training Visit	24
25	4.1 Insulin Pump and DiAs.....	25
26	4.2 Continuous Glucose Monitor.....	25
27	4.3 Blood Glucose Meter and Strips.....	26
28	4.4 Ketone Meter and Strips	27
29	4.5 Study Devices Accountability Procedures.....	27

30	Chapter 5: AIDANET At-Home Period	28
31	5.1 AIDANET use at home.....	28
32	5.2 Pre-Hotel Check-In Visit	28
33	Chapter 6: Supervised Hotel Fully Closed-Loop Period	29
34	6.1 Hotel Session	29
35	6.2 Qualifications and Role of the Staff.....	29
36	6.3 Hotel Session Check-In.....	29
37	6.4 Study Meals	30
38	6.5 Hotel Session Activities.....	30
39	6.6 Glycemic Treatment Guidelines	30
40	6.7 Hotel Session Discharge	31
41	6.8 Other Issues.....	31
42	Chapter 7: AIDANET+BPS_RL At-Home Period	32
43	7.1 AIDANET+BPS_RL use at home	32

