2.2 Specific Aims and Hypotheses

Aim 1: To evaluate the performance (safety, efficacy) of AIDANET+ BPS_RL used as FCL.

Hypothesis: AIDANET+ BPS_RL use will result in equivalent or better Time in Range (TIR) than AIDANET (including current BPS) during two 18-hour hotel sessions (randomized crossover).

[figure not shown]
Aim 2: To evaluate the safety and efficacy of AIDANET+ BPS_RL at home.

Hypothesis: AIDANET+ BPS_RL use will result in equivalent or better TIR than AIDANET alone, during a week of At-Home use (repeated measures).

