2.3 Study Design

This study is a randomized cross-over trial comparing AIDANET (including the current BPS) to AIDANET+ BPS_RL which includes the new BPS_RL (Figure 1). A week of AIDANET control at home will be followed by a two-night hotel session when participants will cross over from AIDANET to AIDANET+ BPS_RL and vice versa and will use new BPS_RL for a subsequent AIDANET+ BPS_RL week at home. For the majority of time, the participants will not announce meal ingestion to the system, thereby using the system in FCL mode of operation. However, the AIDANET system is designed to also work in hybrid closed-loop (HCL) mode with carbohydrate announcement, if requested by the user; thus, users will be allowed to enter carbohydrate amounts, which will be recorded by the system.

AIDANET+BPS_RL Study Timeline

Completion goal **N=16** subjects

Figure 1: Study Design

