2.5 Timing of Device Use

Following screening and randomization, all participants will be trained on the use of the study equipment and AIDANET algorithm. Participants will be connected to a Dexcom G6 sensor and the Tandem t:AP pump, which will be connected to the DiAs platform. AIDANET will be started on DiAs, and the participants will be trained how to use the Dexcom G6 sensor (if using Dexcom G7 in their AID system), the Tandem t:AP pump, and DiAs/AIDANET (see Table 1 and Figure 1). The t:AP pump will be programmed with back up parameters determined by the study investigator(s). Once started, the participants will have their glucose values managed through use of this system during the At-Home and hotel periods.

One-Week AIDANET: All participants will collect approximately one week of AIDANET baseline data. During this period, participants will generally use AIDANET in FCL mode. The DiAs Remote Monitoring will be on, supervised by study personnel.

Hotel Session: Participants will arrive at the hotel in the afternoon (prior to dinner). Those randomized to Group A will continue to use their AIDANET system. Those randomized to Group B will be switched to the AIDANET+BPS_RL system. Because AIDANET and AIDANET+BPS_RL have identical user interfaces and only the priming bolus calculation is changed “under the hood,” no additional training will be needed.

One-Week AIDANET+ BPS_RL: Participants will continue to use the Tandem t:AP pump, DiAs platform running the AIDANET+ BPS_RL, and Dexcom G6 CGM for glucose control for 7 days/6

243 nights during this period. The DiAs Remote Monitoring will be on, supervised by study personnel.
244 At the end of this period participants will return to their usual diabetes therapy.

245 **2.6 Meal Testing**

246 During the home study, participants will be instructed to consume their usual diet and will not be
247 required to record the timing of the meals. 2.3

248 **2.7 Study Devices Download**

249 Data from the study devices will be captured in real-time by the remote monitoring server for the
250 DiAs system. In addition, study devices will be downloaded at the end of the home visits.

251 **2.8 Study System Issues**

252 If the CGM signal becomes unavailable for more than 20 minutes consecutively, closed loop will
253 not operate to automatically adjust insulin delivery. If the CGM is not connected, the system will
254 revert to the usual open loop function of the pump and deliver insulin with the pre-programmed

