7.1 AIDANET+BPS_RL use at home

Upon discharge on Day 3 of the hotel period, participants will begin a 7-day/6-night Remote Monitored At-Home stage of the study. Participants will continue to wear the FCL research system as initiated during the hotel period. Participants will be instructed to eat approximately 3 freely chosen meals per day without announcing them to the system. Participants will be instructed to participate in their usual level of physical activity. Participants will complete the study after lunch on overall study Day 9 (Day 7 of the home portion), at which point they will return to use of their usual diabetes care.

Approximately 24-48 hours after initiating the system, the study team will contact the participant via phone/email/text/video to assess adverse events, adverse device effects, and device issues. If the participant chooses, this visit can occur at the clinical site. The study team will verify the following information:

1. Review system use
2. Inquire about any changes to the participant's medical history
3. Inquire about any changes to the participant's medication
4. Review of CGM data
5. Review of hypoglycemic events
6. Review of hyperglycemic events

Any other relevant contacts during the week will be recorded on the CRF and summarized as appropriate (e.g. contact that is not a scheduling or supplies issue will not be recorded).

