12.1 Design and Randomization

This pilot study aims to demonstrate the safety and feasibility of the AIDANET+BPS_RL algorithm, which replaces with a new BPS_RL the bolus priming module of our AIDANET system described in IDE #G240236, which was approved by the FDA on October 10, 2024.

As presented in Figure 1, this study is a randomized cross-over trial comparing AIDANET to AIDANET+BPS_RL, which includes the new BPS_RL. A week of AIDANET control at home will be followed by a two-night hotel stay where participants will cross over from AIDANET to AIDANET+BPS_RL and vice versa and will learn how to operate the new BPS_RL for a subsequent AIDANET+BPS_RL week at home. The participants are not expected or encouraged to announce meals to the system, thus the system will run in fully-automated closed loop (FCL) mode.

Eligible participants will be randomized to two groups, A and B, which differ only by the order of administration of AIDANET or AIDANET+BPS_RL during the hotel section of the study. The remaining procedures are identical for both groups A and B. The randomization list will use a sequence of computer-generated pseudorandom Bernoulli trials and will aim to balance groups by baseline HbA1c (Figure 1).

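### Section 5.1 tells participants to keep their normal insulin routine in the AIDANET home week, which conflicts with the intended unannounced use and could bias the Aim 2 comparison

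*Combined protocol and SAP*

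**What the plan says.** The two home weeks carry different instructions.

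- AIDANET week (section 5.1): "Participants will be instructed to follow their normal routine involving diet, exercise, and insulin administration during this week". Nothing in 5.1 asks participants to leave meals unannounced.
- AIDANET+BPS_RL week (section 7.1): "Participants will be instructed to eat approximately 3 freely chosen meals per day without announcing them to the system".

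Elsewhere the plan describes mainly unannounced use in both weeks.

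- Section 2.5, on the AIDANET week: "During this period, participants will generally use AIDANET in FCL mode".
- Section 12.1, on the study as a whole: "The participants are not expected or encouraged to announce meals to the system".
- Section 2.3 expects meals to go unannounced most of the time but keeps a hybrid option: "users will be allowed to enter carbohydrate amounts, which will be recorded by the system".
- Table 2 lists the metric "Unannounced Meals: % CGM>250 mg/dL" for the AIDANET home week as well as for the hotel and the BPS_RL home week.

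Aim 2 in section 2.2 rests on comparing these weeks. Its hypothesis is that "AIDANET+ BPS_RL use will result in equivalent or better TIR than AIDANET alone, during a week of At-Home use". Sections 12.3 and 12.4 base that comparison on the last 3 days of each home week. Every participant has the AIDANET week first; only the order within the hotel stay is randomized (12.1).

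**The concern.** The bolus-priming module is meant to do the work of a meal bolus that the user does not give. Whether users announce meals is therefore the behaviour that most needs to be the same in both weeks. Inclusion criterion 3 requires use of an automated insulin delivery system within the last three months. For many such people, normal insulin administration plausibly includes announcing or bolusing for meals.

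If 5.1 is followed on that reading, some AIDANET-week meals will be covered by user boluses while BPS_RL-week meals mostly will not. With a fixed order, that difference cannot be separated from the change of algorithm. It would probably raise TIR in the AIDANET week and so understate BPS_RL. For time below range the direction is open, because meal boluses could raise or lower it.

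The covariates in 12.4 (HbA1c, gender and first-week TIR are the examples given) do not measure announcing, and no planned analysis uses the recorded carbohydrate entries. Fixed order already confounds Aim 2 with period; the 5.1 wording adds a second difference that is easy to avoid.

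**Working it through.** **Comparing the sections**

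| Feature | AIDANET home week | AIDANET+BPS_RL home week |
|---|---|---|
| Instruction to participants | Normal routine, including insulin (5.1) | About 3 meals a day, unannounced (7.1) |
| Intended mode | Generally fully closed loop (2.5); announcing not expected (12.1) | Fully closed loop (12.1) |
| Carbohydrate entry | Allowed and recorded (2.3) | Allowed and recorded (2.3) |
| Position | Always first | Always last |
| Data analysed | Last 3 days (12.3) | Last 3 days (12.3) |

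Only the instruction row conflicts with the plan's own intent. Because carbohydrate entry is allowed in both weeks, 7.1 is an instruction and not a ban.

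**Size of a possible bias**

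The plan gives no figure for this, so there is none to reproduce. Three inputs are needed, and none is in the documents:

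- p1, p2: the shares of meals announced in the analysed 3 days of weeks 1 and 2;
- d: the TIR gain, in percentage points, from announcing all meals rather than none, taken as proportional to the share announced and equal under both algorithms.

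With a true algorithm effect Δ, the expected week-2 minus week-1 difference is Δ + p2·d − p1·d = Δ − (p1 − p2)·d. The bias is therefore −(p1 − p2)·d.

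| p1 − p2 | d = 2 | d = 5 | d = 10 |
|---|---|---|---|
| 0 | 0 | 0 | 0 |
| 0.1 | −0.2 | −0.5 | −1.0 |
| 0.3 | −0.6 | −1.5 | −3.0 |

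In terms of meals, 3 a day (the 7.1 figure, assumed for week 1 too) over 3 days gives 9 meals per participant. A difference of 0.1 is 0.1 × 9 = 0.9, about one extra announced meal per participant. A difference of 0.3 is 0.3 × 9 = 2.7 meals.

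**A yardstick**

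Section 12.2 aims for f = 0.2 on the hotel outcome and gives N = 50 for a later study. With an assumed within-person correlation of 0.5, the standardized paired difference is 2 × 0.2 / √(2 × 0.5) = 0.40. At two-sided 5% and 80% power (also assumed), the normal approximation gives ((1.960 + 0.842)/0.40)² ≈ 49.1, rounded up to 50, which matches the plan.

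If the SD of paired TIR differences is assumed to be 10 points, 0.40 SD is 4.0 points. Against that, a bias of −0.5 is one eighth of the target gain and −3.0 is three quarters of it. This only gives scale: the target belongs to the hotel outcome, and the SD is assumed.

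**The case against.** The strongest reply is that 5.1 never tells anyone to announce a meal. The sentence before it puts participants on the study equipment running AIDANET, so a normal routine can mean ordinary life on that system. Section 2.5 says this week is generally fully closed loop. Participants also have 4 to 8 hours of training first (chapter 4), and system use is reviewed 24 to 48 hours after the start. Aim 2 is a secondary, fixed-order contrast in a pilot with stated power below 50% (12.6). If the TIR bias runs as suggested, it cannot create a false benefit for BPS_RL. Boluses per day, total insulin and operational modes are already to be captured.

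Much of this stands. The conflict lies in the natural reading of 5.1 and not in an explicit order to bolus. The direction for TIR is likely but not documented, and the low end of the range is the more plausible. Table 2 is weak support, since an unannounced-meal metric also fits a week with both kinds of meal.

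It does not remove the problem. Sections 2.3, 2.5 and 12.1 state intent, while 5.1 states what participants are told. The content of the training on announcing is not described. The point about a conservative bias covers TIR only, since time below range could shift either way. An existing period confound is no reason to keep a second, removable difference.

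**Conclusion.** The concern holds. As written, 5.1 conflicts with the unannounced use intended by 2.3, 2.5 and 12.1 and differs from the instruction in 7.1 on a behaviour central to the comparison. It could bias Aim 2, probably against BPS_RL on TIR. The size is unknown: zero if week 1 is run strictly fully closed loop, and −0.2 to −3.0 points over the non-zero values assumed for p1 − p2 (0.1 and 0.3) and d (2 to 10 points).

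The primary outcome is not affected by this point, because its order is randomized and hotel meals are unannounced in both sessions (6.4). The change is worth making because it is nearly free, not because a large bias has been shown. Confidence is moderate, since the consequence depends on how participants and trainers read one sentence.

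**What to change.** 1. In 5.1, replace the sentence with the 7.1 instruction: about three freely chosen meals a day, not announced to the system, with usual diet and activity.
2. In the 12.3 tabulation, report for the last 3 days of each home week the carbohydrate entries per day, announced grams per day and user-initiated boluses per day. Counts per day are the right unit: section 2.6 does not require home meal times to be recorded, so a share of meals announced cannot be calculated. Any remaining imbalance is then visible when Aim 2 is interpreted.

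The cost is one sentence and a few table rows. The system already records carbohydrate entries, and boluses per day are already captured, so the additions are those entries and the split of user-initiated from automated dosing. Sample size and visits do not change. Users may still enter carbohydrate under 2.3, and the three-meal wording only matches what week 2 already says. The first change matters most; the second is optional support.
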